Appendix 2. Clinical Laboratory Tests

Laboratory Tests

| | |
|--|---|
| Hematology ^a | Clinical Chemistry ^a |
| Hematocrit | Sodium |
| Hemoglobin | Potassium |
| Erythrocyte count (RBC) | Calcium |
| Mean cell volume | Phosphorus |
| Mean cell hemoglobin | Glucose (random) |
| Mean cell hemoglobin concentration | Blood urea nitrogen (BUN) |
| Leukocytes (WBC) | Uric acid |
| Cell Morphology | Total cholesterol |
| Absolute counts of: | Total protein |
| Neutrophils | Albumin |
| Lymphocytes | Total bilirubin |
| Monocytes | Alkaline phosphatase (ALP) |
| Eosinophils | Aspartate aminotransferase (AST) |
| Basophils | Alanine aminotransferase (ALT) |
| Platelets | Creatinine |
| Urinalysis ^a | Ethanol testing ^c |
| Specific gravity | Urine drug screen ^c |
| pH | QuantiFERON-TB Gold test ^{a,d} |
| Protein | Serology ^d |
| Glucose | Hepatitis B surface antigen |
| Ketones | Hepatitis B core antibody |
| Bilirubin | Hepatitis C antibody |
| Urobilinogen | HIV antibodies |
| Blood | Pregnancy test (serum/urine) ^{e,f} |
| Nitrite | Hormone Panel |
| Microscopic examination of sediment ^b | FSH ^{d,g} |

Abbreviations: FSH = follicle-stimulating hormone; HIV = human immunodeficiency virus; RBC = red blood cells; WBC = white blood cells.

a Results will be validated by the local laboratory at the time of initial testing.

b If clinically indicated, per investigator's discretion.

c Urine drug screen and ethanol level will be performed locally at screening and during admission to the clinical research unit. May be repeated at the discretion of the investigator.

d Performed at screening only.

e Women of childbearing potential only. Serum pregnancy test at screening, urine at other times. A positive urine pregnancy test will be confirmed with a serum pregnancy test.

f Refer to Section 2 for specific sampling timing.

g To be done for women only when needed to confirm postmenopausal status.

Appendix 3. Study Governance, Regulatory and Ethical Considerations

Informed Consent

The investigator is responsible for:

- ensuring that the subject understands the potential risks and benefits of participating in the study.
- ensuring that informed consent is given by each subject or legal representative. This includes obtaining the appropriate signatures and dates on the ICF prior to the performance of any protocol procedures and prior to the administration of investigational product.
- answering any questions the subject may have throughout the study and sharing in a timely manner any new information that may be relevant to the subject's willingness to continue his or her participation in the trial.

Ethical Review

The investigator must give assurance that the ethics committee was properly constituted and convened as required by International Council for Harmonisation (ICH) guidelines and other applicable laws and regulations.

Documentation of EC approval of the protocol and the ICF must be provided to Lilly before the study may begin at the investigative site(s). Lilly or its representatives must approve the ICF before it is used at the investigative site(s). All ICFs must be compliant with the ICH guideline on GCP.

The study site's EC(s) should be provided with the following:

- the current IB and updates during the course of the study
- ICF
- relevant curricula vitae

Regulatory Considerations

This study will be conducted in accordance with:

- 1) consensus ethics principles derived from international ethics guidelines, including the Declaration of Helsinki and Council for International Organizations of Medical Sciences (CIOMS) International Ethical Guidelines
- 2) applicable ICH GCP Guidelines
- 3) applicable laws and regulations

Some of the obligations of the sponsor will be assigned to a third party organization.

Protocol Signatures

The sponsor's responsible medical officer will approve the protocol, confirming that, to the best of his or her knowledge, the protocol accurately describes the planned design and conduct of the study.

After reading the protocol, each principal investigator will sign the protocol signature page and send a copy of the signed page to a Lilly representative.

Final Report Signature

The investigator or designee will sign the clinical study report for this study, indicating agreement with the analyses, results, and conclusions of the report.

The sponsor's responsible medical officer and statistician will sign/approve the final clinical study report for this study, confirming that, to the best of his or her knowledge, the report accurately describes the conduct and results of the study.

Data Quality Assurance

To ensure accurate, complete, and reliable data, Lilly or its representatives will do the following:

- provide instructional material to the study sites, as appropriate.
- provide training to instruct the investigators and study coordinators. This training will give instruction on the protocol, the completion of the eCRFs, and study procedures.
- make periodic visits to the study site.
- be available for consultation and stay in contact with the study site personnel by mail, telephone, and/or fax.
- review and evaluate eCRF data and/or use standard computer edits to detect errors in data collection.
- conduct a quality review of the database.

In addition, Lilly or its representatives will periodically check a sample of the subject data recorded against source documents at the study site. The study may be audited by Lilly and/or regulatory agencies at any time. Investigators will be given notice before an audit occurs.

The investigator will keep records of all original source data. This might include laboratory tests, medical records, and clinical notes. If requested, the investigator will provide the sponsor, applicable regulatory agencies, and applicable ECs with direct access to the original source documents.

Data Collection Tools/Source Data

An electronic data capture system will be used in this study. The site must define and retain all source records and must maintain a record of any data where source data are directly entered into the data capture system.

Study and Site Closure***Discontinuation of Study Sites***

Study site participation may be discontinued if Lilly or its designee, the investigator, or the EC of the study site judges it necessary for medical, safety, regulatory, or other reasons consistent with applicable laws, regulations, and GCP.

Discontinuation of the Study

The study will be discontinued if Lilly or its designee judges it necessary for medical, safety, regulatory, or other reasons consistent with applicable laws, regulations, and GCP.

Appendix 4. Blood Sampling Summary

This table summarizes the approximate number of venipunctures and blood volumes for all blood sampling (screening, safety laboratories, and bioanalytical assays) during the study. Fewer venipunctures and blood draws may actually occur, but this will not require a protocol amendment.

Protocol I6T-MC-AMAL Sampling Summary

| Purpose | Maximum Blood Volume per Sample (mL) | Maximum Number of Blood Samples | Maximum Total Volume (mL) |
|---|--------------------------------------|---------------------------------|---------------------------|
| Screening tests ^a | 14 | 1 | 14 |
| Clinical laboratory tests ^a | 7.5 | 6 | 45 |
| Pharmacokinetics ^b | 2 | 19 | 38 |
| Immunogenicity ^a | 10 | 5 | 50 |
| Pharmacogenetics | 10 | 1 | 10 |
| Total | | | 157 |
| Total for clinical purposes [rounded up to nearest 10 mL] | | | 160 |

a Additional samples may be drawn if needed for safety purposes.

b Includes a potential 3 additional samples.

Leo Document ID = fc0167b0-a4ee-4779-8cf4-e3525d3abfe3

Approver: PPD

Approval Date & Time: 20-Jan-2017 01:30:24 GMT

Signature meaning: Approved

Approver: PPD

Approval Date & Time: 20-Jan-2017 14:57:47 GMT

Signature meaning: Approved

2. ABBREVIATIONS

Abbreviations pertain to the Statistical Analysis Plan (SAP) only (not the tables, figures and listings [TFLs]).

ADA	Anti-drug antibody
AE	Adverse event
AUC	Area under the concentration versus time curve
AUC(0-t _{last})	Area under the concentration versus time curve from time zero to time t, where t is the last time point with a measurable concentration
AUC(0-∞)	Area under the concentration time curve from zero to infinity
%AUC(t _{last} -∞)	Percentage of AUC(0-∞) extrapolated
BQL	Below the quantifiable lower limit of the assay
C _{max}	Maximum observed drug concentration
CI	Confidence interval
CL	Total body clearance of drug calculated after IV administration
CL/F	Apparent total body clearance of drug calculated after extra vascular administration
CRF	Case Report Form
CSR	Clinical Study Report
CRU	Clinical Research Unit
CV	Coefficient of variation
EC	Early Clinical
ECG	Electrocardiogram
ED	Early discontinuation
e.g.	For example (Latin: exempli gratia)
ICH	International Council on Harmonisation
IV	Intravenous
LLOQ	Lower limit of quantification
MedDRA	Medical Dictionary for Regulatory Activities
PK	Pharmacokinetic
QTcB	QT interval corrected using Bazett's formula
QTcF	QT interval corrected using Fridericia's formula
SAP	Statistical Analysis Plan

SC	Subcutaneous
SD	Standard deviation
SOP	Standard Operating Procedure
TFLs	Tables, Figures, and Listings
$t_{1/2}$	Half-life associated with the terminal rate constant (λ_z) in non-compartmental analysis
t_{max}	Time of maximum observed drug concentration
VAS	Visual analog scale
V_{ss}	Volume of distribution at steady state after IV administration
$V_{ss/F}$	Apparent volume of distribution at steady state after extra vascular administration
V_z	Volume of distribution during the terminal phase after IV administration
V_z/F	Apparent volume of distribution during the terminal phase after extra-vascular administration
WHO	World Health Organization

3. INTRODUCTION

This SAP has been developed after review of the Clinical Study Protocol (final version dated 15 December 2016).

This SAP describes the planned analysis of the safety, tolerability and pharmacokinetic (PK) data from this study. A detailed description of the planned TFLs to be presented in the clinical study report (CSR) is provided in the accompanying TFL shell document.

The intent of this document is to provide guidance for the statistical and PK analyses of data. In general, the analyses are based on information from the protocol, unless they have been modified by agreement between Eli Lilly and Company and Covance Early Clinical (EC) Biometrics. A limited amount of information concerning this study (e.g., objectives, study design) is given to help the reader's interpretation. This SAP must be signed off prior to first subject administration for this study. When the SAP and TFL shells are agreed upon and finalized, they will serve as the template for this study's CSR.

This SAP supersedes the statistical considerations identified in the protocol; where considerations are substantially different, they will be so identified. If additional analyses are required to supplement the planned analyses described in this SAP, they may be performed and will be identified in the CSR. Any substantial deviations from this SAP will be agreed upon between Eli Lilly and Company and Covance EC Biometrics and identified in the CSR. Any minor deviations from the TFLs may not be documented in the CSR.

This SAP is written with consideration of the recommendations outlined in the International Council on Harmonisation (ICH) E9 Guideline entitled Guidance for Industry: Statistical Principles for Clinical Trials¹ and the ICH E3 Guideline entitled Guidance for Industry: Structure and Content of Clinical Study Reports².

4. STUDY OBJECTIVES

4.1 Primary Objective

- To evaluate the relative bioavailability of the LY3074828 lyophilized formulation prepared by reconstitution (Reference) and the extemporaneously prepared formulation (subcutaneous [SC] 2 × 1-mL) when administered to healthy subjects by SC injection.

4.2 Secondary Objectives

- To evaluate the relative bioavailability of LY3074828 extemporaneously prepared as the test formulation when the same volume is administered to healthy subjects by SC injection using a single injection (1 × 2-mL) and 2 injections (2 × 1-mL).
- To evaluate the absolute bioavailability of LY3074828 extemporaneously prepared as the test formulation when administered to healthy subjects by SC injection compared to intravenous (IV) infusion.
- To assess the impact of Drug Product formulation changes and number of injections on tolerability of LY3074828.

5. STUDY DESIGN

Study AMAL is a single-center, randomized, parallel-treatment, open-label, Phase 1 single-dose administration study evaluating LY3074828 in 72 healthy subjects.

Screening Period (≤ 4 weeks): Subjects will be evaluated for study eligibility ≤ 28 days prior to enrollment.

Residential Period (2 days): Subjects who fulfill the eligibility criteria will be randomized to 1 of 4 treatments, with 18 subjects randomized to each treatment, as shown below:

- Reference: 250 mg LY3074828; lyophilized reference formulation with $2 \times 1\text{-mL} + 1 \times 1.5\text{-mL}$ SC injections;
- Test SC $2 \times 1\text{-mL}$: 250 mg LY3074828; test formulation with $2 \times 1\text{-mL}$ SC injections;
- Test SC $1 \times 2\text{-mL}$: 250 mg LY3074828; test formulation with $1 \times 2\text{-mL}$ SC injection;
- Test IV: 250 mg LY3074828; test formulation by IV infusion over at least 30 minutes.

Subjects will report to the clinical research unit (CRU) on Day -1 and remain at the CRU until after the scheduled procedures have been completed on Day 2 as defined in the Schedule of Activities (Section 2 of Protocol). After randomization, study drug will be administered by either IV infusion or SC injection in the morning of Day 1 after an overnight fast. Subjects within the same enrollment group may be dosed across several days if required by the site for logistical or other purposes.

Outpatient Follow-up Period (approximately 14 weeks): The follow-up period will include outpatient visits for a total of 12 weeks following Day 1 dose administration to assess tolerability and PK of LY3074828. An end-of-study follow-up visit will be scheduled within 7 to 14 days after the last procedure or upon early discontinuation (ED).

6. TREATMENTS

The following is a list of the study treatment abbreviations that will be used in the TFLs.

Study Treatment Name	Abbreviation	Treatment order in TFL
250 mg LY3074828 reference SC (2×1 mL, 1×1.5 mL)	Reference	1
250 mg LY3074828 test SC (2×1 mL)	Test SC $2 \times 1\text{-mL}$	2
250 mg LY3074828 test SC (1×2 mL)	Test SC 1×2 mL	3
250 mg LY3074828 test IV	Test IV	4

7. SAMPLE SIZE JUSTIFICATION

A total of 72 subjects will be enrolled to ensure that approximately 64 subjects complete the study (16 completers per treatment). The estimated total variability (coefficient of variation) in AUC from time zero to infinity ($AUC[0-\infty]$), AUC from time zero to time t , where t is the last sample with a measurable concentration ($AUC[0-t_{last}]$), and maximum observed drug concentration (C_{max}) was 49%, 49%, and 23%, respectively, in Study AMAA following a single SC dose of 120 mg LY3074828. The coefficient of variation of 49% was used for precision estimates and is assumed for all treatment arms. A sample size of 64 subjects will provide a precision of approximately 28% for the geometric means ratio in $AUC(0 -\infty)$, $AUC(0-t_{last})$, and C_{max} of reference to test in log scale. That is, there is a 90% probability that the half-length of the 90% confidence interval (CI) of the geometric means ratio in log scale is not larger than 28%.

Subjects who are randomized but not administered treatment may be replaced to ensure that approximately 64 subjects may complete the study.

8. DEFINITION OF ANALYSIS POPULATIONS

The “Safety” population will consist of all subjects who received study drug, and have at least one postdose safety assessment.

The “Pharmacokinetic” population will consist of all subjects who received study drug and have evaluable PK data.

All protocol deviations that occur during the study will be considered for their severity/impact and will be taken into consideration when subjects are assigned to analysis populations.

9. STATISTICAL METHODOLOGY

9.1 General

Data listings will be provided for all data that is databased. Summary statistics and statistical analysis will only be presented for data where detailed in this SAP. For continuous data, summary statistics will include the arithmetic mean, arithmetic standard deviation (SD), median, min, max and N; for log-normal data (e.g. the PK parameters: AUCs and C_{max}) the geometric mean and geometric coefficient of variation (CV%) will also be presented. For categorical data, frequency count and percentages will be presented. Data listings will be provided for all subjects up to the point of withdrawal, with any subjects excluded from the relevant population highlighted. Summary statistics and statistical analyses will generally only be performed for subjects included in the relevant analysis population. For the calculation of summary statistics and statistical analyses, unrounded data will be used.

Mean change from baseline is the mean of all individual subjects' change from baseline values. Each individual change from baseline will be calculated by subtracting the individual subject's baseline value from the value at the timepoint. The individual subject's change from baseline values will be used to calculate the mean change from baseline using a SAS procedure such as Proc Univariate.

Data analysis will be performed using SAS® Version 9.3 or greater.

9.2 Demographics and Subject Disposition

Subject disposition will be listed. The demographic variables age, sex, race, ethnicity, country of enrolment, site ID, body weight, height and body mass index will be summarized and listed.

9.3 Pharmacokinetic Assessment

9.3.1 Pharmacokinetic Analysis

Noncompartmental methods applied with a validated software program (Phoenix WinNonlin Version 6.4 or later) to the plasma concentrations of LY3074828 will be used to determine the following PK parameters, when possible:

Parameter	Units	Definition
AUC(0-t _{last})	µg.day/mL	area under the concentration versus time curve from time zero to time t, where t is the last time point with a measurable concentration
AUC(0-∞)	µg.day/mL	area under the concentration versus time curve from zero to infinity
%AUC(t _{last} -∞)	%	percentage of AUC(0-∞) extrapolated
C _{max}	µg/mL	maximum observed drug concentration
t _{max}	Hour	time of maximum observed drug concentration
t _{1/2}	Day	half-life associated with the terminal rate constant (λ_z) in non-compartmental analysis
CL/F	L/day	apparent total body clearance of drug calculated after extra-vascular administration
V _{Z/F}	L	apparent volume of distribution during the terminal phase after extra-vascular administration
V _{ss/F}	L	apparent volume of distribution at steady state after extra-vascular administration
CL	L/day	total body clearance of drug calculated after IV administration
V _Z	L	volume of distribution during the terminal phase after IV administration
V _{ss}	L	volume of distribution at steady state after IV administration
F		absolute subcutaneous bioavailability
F _{rel}		relative bioavailability

Additional PK parameters may be calculated, as appropriate. The software and version used for the final analyses will be specified in the clinical study report. Any exceptions or special handling of data will be clearly documented within the final study report.

Formatting of tables, figures and abbreviations will follow the Eli Lilly Global PK/PD/TS Tool: NON-COMPARTMENTAL PHARMACOKINETIC STYLE GUIDE. The version of the tool effective at the time of PK analysis will be followed.

General PK Parameter Rules

- Actual sampling times will be used in the final analyses of individual PK parameters, except for non-bolus pre-dose sampling times which will be set to zero. For non-bolus, multiple dose profiles, the pre-dose time will be set to zero unless a time deviation falls outside of the protocol blood collection time window which is considered to impact PK parameter derivation.
- C_{\max} and t_{\max} will be reported from observed values. If C_{\max} occurs at more than one time point, t_{\max} will be assigned to the first occurrence of C_{\max} .
- AUC parameters will be calculated using a combination of the linear and logarithmic trapezoidal methods (linear-log trapezoidal rule). The linear trapezoidal method will be applied up to t_{\max} and then the logarithmic trapezoidal method will be used after t_{\max} . The minimum requirement for the calculation of AUC will be the inclusion of at least three consecutive plasma concentrations above the lower limit of quantification (LLOQ), with at least one of these concentrations following C_{\max} . AUC($0-\infty$) values where the percentage of the total area extrapolated is more than 20% will be flagged. Any AUC($0-\infty$) value excluded from summary statistics will be noted in the footnote of the summary table.
- Half-life ($t_{1/2}$) will be calculated, when appropriate, based on the apparent terminal log-linear portion of the concentration-time curve. The start of the terminal elimination phase for each subject will be defined by visual inspection and generally will be the first point at which there is no systematic deviation from the log-linear decline in plasma concentrations. Half-life will only be calculated when a reliable estimate for this parameter can be obtained comprising of at least 3 data points. If $t_{1/2}$ is estimated over a time window of less than 2 half-lives, the values will be flagged in the data listings. Any $t_{1/2}$ value excluded from summary statistics will be documented in the footnote of the summary table.
- A uniform weighting scheme will be used in the regression analysis of the terminal log-linear portion of the concentration-time curve.
- The parameters based on observed C_{last} will be reported.

Individual PK Parameter Rules

- Only quantifiable concentrations will be used to calculate PK Parameters with the exception of special handling of certain concentrations reported below the lower limit of quantitation (BQL). Plasma concentrations reported as BQL will be set to a value of zero when all of the following conditions are met:
 - The compound is non-endogenous.

- The samples are from the initial dose period for a subject or from a subsequent dose period following a suitable wash-out period.
- The time points occur before the first quantifiable concentration.
- All other BQL concentrations that do not meet the above criteria will be set to missing.
- Also, where two or more consecutive concentrations are BQL towards the end of a profile, the profile will be deemed to have terminated and therefore any further quantifiable concentrations will be set to missing for the calculation of the PK parameters unless it is considered to be a true characteristic of the profile of the drug.

Individual Concentration vs. Time Profiles

- Individual concentrations will be plotted utilizing actual sampling times.
- The terminal point selections will be indicated on a semi-logarithmic plot.

Average Concentration vs. Time Profiles

- The average concentration profiles will be graphed using scheduled (nominal) sampling times.
- The average concentration profiles will be graphed using arithmetic average concentrations.
- The pre-dose average concentration for single-dose data from non-endogenous compounds will be set to zero. Otherwise, only quantifiable concentrations will be used to calculate average concentrations.
- Concentrations at a sampling time exceeding the sampling time window specified in the protocol, or $\pm 10\%$, will be excluded from the average concentration profiles.
- Concentrations excluded from the mean calculation will be documented in the final study report.
- A concentration average will be plotted for a given sampling time only if 2/3 of the individual data at the time point have quantifiable measurements that are within the sampling time window specified in the protocol or $\pm 10\%$. An average concentration estimated with less than 2/3 but more than 3 data points may be displayed on the mean concentration plot if determined to be appropriate and will be documented within the final study report.

Treatment of Outliers during Pharmacokinetic Analysis

Application of this procedure to all PK analyses is not a requirement. Rather, this procedure provides justification for exclusion of data when scientifically appropriate. This procedure describes the methodology for identifying an individual value as an outlier for potential exclusion, but does not require that the value be excluded from analysis. The following methodology will not be used to exclude complete profiles from analysis.

Data within an Individual Profile

A value within an individual profile may be excluded from analysis if any of the following criteria are met:

- For PK profiles during multiple dosing, the concentration of the pre-dose sample exceeds all measured concentrations for that individual in the subsequent post-dose samples.
- For PK profiles during single dosing of non-endogenous compounds, the concentration in a pre-dose sample is quantifiable.
- For any questionable datum that does not satisfy the above criteria, the profile will be evaluated and results reported with and without the suspected datum.

Data between Individual Profiles

1. If $n < 6$, then the dataset is too small to conduct a reliable range test. Data will be analyzed with and without the atypical value, and both sets of results will be reported.
2. If $n \geq 6$, then an objective outlier test will be used to compare the atypical value to other values included in that calculation:
 - a. Transform all values in the calculation to the logarithmic domain.
 - b. Find the most extreme value from the arithmetic mean of the log transformed values and exclude that value from the dataset.
 - c. Calculate the lower and upper bounds of the range defined by the arithmetic mean $\pm 3 \times \text{SD}$ of the remaining log-transformed values.
 - d. If the extreme value is within the range of arithmetic mean $\pm 3 \times \text{SD}$, then it is not an outlier and will be retained in the dataset.
 - e. If the extreme value is outside the range of arithmetic mean $\pm 3 \times \text{SD}$, then it is an outlier and will be excluded from analysis.

If the remaining dataset contains another atypical datum suspected to be an outlier and $n \geq 6$ following the exclusion, then repeat step 2 above. This evaluation may be repeated as many times as necessary, excluding only one suspected outlier in each iteration, until all data remaining in the dataset fall within the range of arithmetic mean $\pm 3 \times \text{SD}$ of the log-transformed values.

Reporting of Excluded Values

Individual values excluded as outliers will be documented in the final report. Approval of the final report will connote approval of the exclusion.

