10. INTERIM ANALYSES

The Lilly study team and investigator will be unblinded. Data may be accessed and analyzed while the trial is ongoing, but no changes to the study design are planned. An assessment committee will not be formed.

Interim analysis is scheduled to occur when safety and PK data through approximately Day 57 (8 weeks postdose) become available from enrolled subjects from each treatment. The purpose of the interim analysis is to: trigger Chemistry, Manufacturing, and Control processes with respect to LY3074828 formulation; trigger the formal bridging study; and to inform dose selection for Phase 3 first registration.

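### SAP 9.3.1 allows between-subject PK values to be dropped by a repeated 3-SD test with no named cause, and does not require the all-data result when n is 6 or more

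*SAP*

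**What the plan says.** The outlier procedure is in SAP 9.3.1. Its preamble makes use optional: the procedure justifies exclusion where that is scientifically appropriate, a term left undefined, and it "does not require that the value be excluded from analysis". The preamble also sets a limit: "The following methodology will not be used to exclude complete profiles from analysis".

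For values compared between subjects there are two branches.

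- **n below 6:** "Data will be analyzed with and without the atypical value, and both sets of results will be reported".
- **n of 6 or more:** an objective test is used to "compare the atypical value to other values included in that calculation". The values are logged, the most extreme one is set aside, and it is compared with the mean ± 3 SD of the remainder. If it lies outside, "then it is an outlier and will be excluded from analysis". Further values can follow: "This evaluation may be repeated as many times as necessary, excluding only one suspected outlier in each iteration".

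For a questionable point inside one subject's profile, "the profile will be evaluated and results reported with and without the suspected datum".

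Excluded values must be documented in the final report, and approval of the report counts as approval of the exclusion. SAP Section 10 states: "The Lilly study team and investigator will be unblinded". Protocol 10.3 bases the PK analyses on all data from every dosed subject with evaluable PK data and contains no outlier rule. SAP Section 3 promises to identify substantial departures from the protocol; Section 11 declares none.

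**The concern.** With 18 subjects randomized and 16 expected to complete per arm, the branch for n of 6 or more always governs the arm comparisons. It is the only one of the three situations above in which the all-data result is not required. A value can leave on distance alone, without evidence that anything went wrong with dosing, sampling or the assay. Whether to invoke the test, and whether to act on it, is left to judgement in an open-label trial with no blinded outlier review described.

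Three points are also left open:

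1. The preamble says exclusion is not required, while the test step says the value will be excluded.
2. The set against which a value is compared is not defined. It could be one arm, pooled arms or model residuals.
3. The bar on excluding complete profiles does not say whether it protects a subject's AUC or Cmax in the Section 9.3.2 model.

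If the rule does act on AUC or Cmax in the primary comparison, removing a genuine tail value shrinks the residual variance and shifts the geometric mean ratio. The 90% CI can then cover less often than stated, and the reader need not be shown the all-data interval. The documents set no equivalence margin. However, the interim results are meant to trigger manufacturing steps and the bridging study and to inform Phase 3 dose selection (Protocol 10.3.6, SAP Section 10).

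**Working it through.** **Inputs.** CV 49% for all arms and 16 completers per arm (Protocol 10.1, SAP Section 7). Threshold of mean ± 3 SD of the remaining log values, repeated while n is at least 6 (SAP 9.3.1). A four-arm linear model on the log scale with 90% CIs (SAP 9.3.2).

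**Assumptions.** The data are log-normal with no errors. The rule acts on the parameter entering the Section 9.3.2 model. Every extreme value is tested. The last assumption makes the rates below upper-end, because the SAP needs someone first to call a value atypical.

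**Step 1: baseline precision.** The SAP states no error rate for the rule, so the reference is the planned CI width.

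- Log-scale SD = √ln(1 + 0.49²) = 0.464.
- Expected half-width = t(0.95, 60 df) × 0.464 × √(2/16) = 0.274.

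This is close to the plan's 28% read as an expected half-width. The plan's claim of 90% probability is a separate matter and is not used here.

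**Step 2: how often a clean arm loses a value.** Comparing one value with the mean ± 3 SD of the other 15 is a t test on 14 df:

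- t = 3/√(1 + 1/15) = 2.905, two-sided p = 0.0115.
- Over 16 values: 16 × 0.0115 ≈ 0.185 per arm (0.182 at n = 18).
- At least one of two arms: 1 − (1 − 0.185)² ≈ 0.34.

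Simulation of the repeated rule gives 18.5% of arms and 33–34% of two-arm comparisons.

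**Step 3: effect of one exclusion.** Dropping a value 3 SD from the mean of the others changes the ratio by a factor of exp(3 × 0.464/16) = 1.09 at n = 16, or 1.08 at n = 18.

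**Step 4: effect on the 90% CI.** Two simulation seeds, 20,000 four-arm trials per scenario, four-arm pooled variance, true ratios 1.0 and 0.8:

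| Comparison set | Coverage | Mean half-width | Primary comparisons losing a value | Coverage when a primary arm loses a value |
|---|---|---|---|---|
| No rule (all data) | 89.8–90.1% | 0.273 | none | not applicable |
| Within arm | 86.9–87.1% | 0.264 | 33% | 82.5–83.0% |
| Model residuals | 88.4–88.5% | 0.268 | 14% | 80.7–81.1% |
| Three SC arms pooled, IV alone | 89.4–90.0% | 0.266 | 15–16% | 89.2–91.2% |
| Two primary arms pooled | 89.5–90.7% | 0.270 | 19% | 89.4–92.9% |

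When a primary arm loses a value, the log ratio moves on average by 0.078 (within arm) to 0.088, which is about 8–9%. Separate within-arm runs agree: 87.0–87.2% with the four-arm variance, and 86.6% against 89.9% untrimmed with a two-arm variance. In the trials where a within-arm exclusion occurs, the trimmed CI covers about 82–83%, while the all-data CI in the same trials covers 90–91%.

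**Step 5: sensitivity.**

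- Within-arm rule invoked in a random half of arms: coverage 88.5–88.6%. In a quarter of arms: 89.2–89.3%.
- Heavier tails (t with 4 df, assumed; two-arm variance): 44–46% of arms lose a value, and coverage is about 86% against about 90% on all data.

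**The case against.** The strongest objection is about reach. The rule sits in the noncompartmental section; Section 9.3.2, which defines the model, does not mention it. A subject's AUC or Cmax summarizes that subject's profile, so the bar on excluding complete profiles may be meant to protect it. On that reading the effect on the primary CI is zero. This stands as a limit on the size of the problem, but the SAP does not say which reading applies, and exclusion from analysis is worded without restriction.

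Safeguards also exist. The threshold, log scale and stopping point are fixed in advance. Use is optional, exclusions are documented, excluded AUC(0-∞) values are footnoted, and all databased data are listed, so a reader might rebuild the all-data estimate. Neither document says who applies the rule; that it is an unblinded team is inferred from the open-label design and SAP Section 10. These points are fair. Even so, a list of excluded values is not the all-data ratio and CI, and what is fixed in advance is the test, not when to invoke it, on which set, or whether to act.

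The effect is modest. On clean data, within-arm trimming adds no average bias, and the root mean square error of the log ratio rises only from 0.163 to 0.171. Trimming can also help with bad data. With one assumed five-fold-low value in a primary arm, bias was −0.10 on all data and −0.02 trimmed, and root mean square error was 0.193 and 0.183. Trimmed coverage was still lower, at 85% against 87%. This supports showing both results; it does not support showing the trimmed one alone.

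The protocol-consistency point is weak by itself. An optional data-handling rule need not redefine an analysis set limited to evaluable data, and Section 3 asks only for substantial differences to be identified.

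**Conclusion.** The concern holds. For every planned arm, SAP 9.3.1 permits removal of a between-subject value on distance alone and does not require the untrimmed result, although the same section requires it in the two neighbouring situations. The loss of coverage from the nominal 90% is 0 to about 3 points with mechanical use on clean log-normal data. It is largest for a within-arm comparison set and near zero when arms are pooled. These are rates under stated assumptions, not a forecast: they require the rule to reach AUC or Cmax in the Section 9.3.2 model, and they shrink if it is seldom invoked. The more telling result is conditional. When a within-arm exclusion happens on clean data, the all-data interval keeps its coverage and the trimmed one does not, yet only the trimmed one need be reported. The change should be made because it is cheap and removes an avoidable doubt about the primary estimate. The wording conflict and the silence of Section 11 are minor.

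**What to change.** In SAP 9.3.1 and 9.3.2:

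- State that the main analyses of AUC(0-∞), AUC(0-t_last) and Cmax use all evaluable values, with exclusion only for a documented dosing, sampling or assay error.
- Report the 3-SD-trimmed result as a sensitivity analysis, with both sets of results at every n. This extends the existing practice for n below 6.
- Define the comparison set for the 3-SD test.
- Say whether the bar on excluding complete profiles covers a subject's AUC or Cmax.
- Reconcile the optional wording of the preamble with the mandatory wording of the test step, and list the rule in Section 11.

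The cost is SAP text and one extra model run per parameter with a flagged value. The downside is a slightly wider main CI when a real extreme value is kept: mean half-width about 0.273 instead of 0.264 to 0.270 on the log scale.
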